2.4.2 Clinical Documentation

Except for nasolabial folds treatment^{4,5} Perlane-Lido also has been proven safe and efficacious for cheek augmentation and correction of age-related midface contour deficiencies in a clinical trial⁶ (MA-1400-05) performed in US. Perlane-Lido is approved under the brand name Restylane® Lyft with Lidocaine in US.

The study was an evaluator-blinded, no treatment controlled study of 200 subjects who were randomized in a 3:1 ratio to receive Perlane-Lido in the midface or no treatment at baseline. The primary effectiveness objective was to identify if Perlane-Lido was more effective in midface augmentation than no treatment as determined by the blinded evaluator's assessment of midface fullness using the Medicis Midface Volume Scale (MMVS) at Month 2 following baseline/Day 0.

In the Perlane-Lido group, 88.7% (133/150 subjects) were MMVS responders in the right and left midface combined. In the no treatment group at Month 2, the proportion of MMVS responders from baseline was 16.0% (8/50 subjects). The difference in the proportion of

 GALDERMA	Title 43CH1507 Perlane Lido midface study protocol	Doc id MA-30843
--	---	----------------------------------

Effective date: 2016-09-07 11:57

Effective

Version: 4.0

MMVS responders from baseline for right and left midface combined, between the Perlane-Lido and no treatment groups, was statistically significant ($p<0.001$) in favor of Perlane-Lido treatment; therefore, the primary effectiveness assessment was met.

The proportion of MMVS responders was also statistically significant at all other evaluation time points through Month 12 for both the blinded evaluator **CCI** [REDACTED], as outlined in the secondary objectives.

The study also indicates that the safety profile of Perlane-Lido is maintained. The majority of events were mild, considered tolerable and resolved in 2 – 7 days. Bruising tended to have a longer duration with the majority of subjects resolving between 8 and 14 days. Two subjects (1%, 2/199) reported four serious adverse events (SAEs) that were considered to be related to the device and/or the procedure. One subject reported implant site inflammation (late onset inflammatory reactions) in both cheeks at separate times. The second subject experienced implant site hematomas in the right cheek and implant site infection/abscess. Treatment of the SAEs included NSAIDs, antibiotics, incision and drainage and, hyaluronidase. All events resolved.

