4.2 Number of Subjects

The study will be performed at approximately 5 sites in China and approximately 168 subjects will be enrolled.

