1.1.2 Number of subjects and randomization

Approximately 148 subjects will be randomized in a 3:1 ratio to treatment with Restylane Perlane Lidocaine (Perlane-Lido) or to no treatment. The randomization will be stratified by site.

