3.3.2 Handling of missing data

Number of missing values will be summarized and reported as appropriate. The baseline observation carried forward (BOCF) method will be used as the primary imputation method to handle missing data on MMVS up to the Month 6 visit in the FAS analysis set. This strategy is a conservative approach as it treats subjects with missing data as non-responders. Impact of missing data on the primary analysis for Month 6 endpoint will be evaluated by performing sensitivity

	Title Statistical Analysis Plan 43CH1507	Doc id MA-32268
--	---	----------------------------------

Effective date: 2017-04-21 09:20

Effective

Version: 1.0

analysis based on the PP population. In addition, missing data for the primary analysis will also be handled using the multiple imputation (MI) method.

All other endpoints will be analyzed on available data, i.e. no imputations will be done.

If the baseline value is missing, the screening value will be used instead.

Use of MI

The imputation using MI will assume a Missing Completely at Random (MAR) mechanism. The MI procedure of the SAS® system will be used to generate five sets of data with missing values imputed from observed data. It is expected that the pattern of missing data will be monotonic, with slight deviations being corrected by the Markov Chain Monte Carlo (MCMC) method of the MI procedure. Linear regression will be employed to model the missing MMVS score, with the following covariates included in the imputation model: treatment and non-missing data from earlier time points (baseline CCI [REDACTED]). The imputed datasets will be analyzed using the methodology described for the primary analysis of responder rates at Month 6. The results from the analysis of the multiple imputed datasets will be presented as appropriate. The seed number to be used will be 431507 (the clinical trial number of this study, with the letters removed).

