3.3.3 Primary analysis

The responder rate will be calculated for each group at Month 6 based on the blinded evaluator's assessment. CCI [REDACTED]

CCI [REDACTED]

In addition, to evaluate the impact of missing data, the primary analysis will be re-run using the PP analysis set.

Site effects will be explored by using descriptive statistics of the treatment effects by site (estimates and confidence intervals of the response rates within site).

Effective

Effective date: 2017-04-21 09:20

Version: 1.0

 GALDERMA	<small>Title</small> Statistical Analysis Plan 43CH1507	<small>Doc id</small> MA-32268

CCI
		

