Table A 37. Time to onset (days) of related TEAEs, by MedDRA System Organ Class and Preferred Term (Safety).....	31
Table A 38. Action taken due to related TEAEs by MedDRA System Organ Class and Preferred Term (Safety).....	32
Table A 39. Unrelated TEAEs by MedDRA System Organ Class, Preferred Term and intensity (Safety).....	32

[figure not shown]

Table of figures

Figure A 1. Difference in MMVS responder rate (left and right midface combined) by site at Month 6, Blinded Evaluator (FAS)	16
---	----

[figure not shown]

Effective date: 2017-04-21 09:20

Effective

Version: 1.0

 GALDERMA	<small>Title</small> Statistical Analysis Plan 43CH1507	<small>Doc id</small> MA-32268
---	---	--

- Figure A 10. Proportion of subjects affected by a specific event (to any intensity level) after initial treatment (Safety) 35
- Figure A 11. Proportion of subjects affected by a specific event (to any intensity level) after touch-up (Safety) 35

 GALDERMA	Title Statistical Analysis Plan 43CH1507	Doc id MA-32268
---	---	--------------------

Table A 1. Subject disposition (all subjects)

Number of subjects		Perlane-Lido	Control	Total
Screened		-	-	xx
Screening failures				xx (%)
Randomized		xx	xx	xx
Completed primary endpoint		xx (%)	xx (%)	xx (%)
Completed		xx (%)	xx (%)	xx (%)
Withdrawn		xx (%)	xx (%)	xx (%)
Reason for withdrawal	Withdrawn consent	xx (%)	xx (%)	xx (%)
	Lost to follow-up	xx (%)	xx (%)	xx (%)
	Medical reason	xx (%)	xx (%)	xx (%)
	Other	xx (%)	xx (%)	xx (%)

% screening failures is based on total number of screened subjects.

% I/E criteria not met and withdrawn consent is based on the number of screening failures.

In all other cases: % is based on the number of randomized subjects.

Table A 2. Analysis populations (all randomized subjects)

Site	Subject Number	Safety		FAS		PP	
		n	%	n	%	n	%
Site 1	101-1xx	xx	xx.x	xx	xx.x	xx	xx.x
Site 2	201-2xx	xx	xx.x	xx	xx.x	xx	xx.x
Site x	x01-xxx	xx	xx.x	xx	xx.x	xx	xx.x
Total (N)	-	xx	100.0	xx	100.0	xx	100.0

% = n/N*100

 GALDERMA	Title Statistical Analysis Plan 43CH1507	Doc id MA-32268
---	--	----------------------------------

Table A 3. Subject accountability (all subjects in Perlane-Lido group)

Number of subjects	Observed	Missed	Withdrawals	Continuing on study
Baseline/initial treatment	xx	xx	xx	xx
4W follow-up/optional touch-up	xx	xx	xx	xx
4W follow-up	xx	xx	xx	xx
3M after last treatment	xx	xx	xx	xx
6M after last treatment	xx	xx	xx	xx
9M after last treatment	xx	xx	xx	xx
12M after last treatment	xx	xx	xx	xx

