 GALDERMA	Title Statistical Analysis Plan 43CH1507	Doc id MA-32268
---	---	--------------------

Table A 16. MMVS responder rate by treatment and side of the face at Month 6, Blinded Evaluator (FAS)

Assessment/Time Point	Treatment Group	# of Subjects in FAS	# of Responders	Proportion of Responders	95% Confidence Interval	P-Value
Right and Left Midface Combined at Month 6	Perlane-Lido	Xx	Xx	X.XX	X.XX, X.XX	
	Control	Xx	Xx	X.XX	X.XX, X.XX	
	Difference	-	-	X.XX	X.XX, X.XX	X.XX
Right Midface at Month 6	Perlane-Lido	Xx	Xx	X.XX	X.XX, X.XX	
	Control	Xx	Xx	X.XX	X.XX, X.XX	
	Difference	-	-	X.XX	X.XX, X.XX	X.XX
Left Midface at Month 6	Perlane-Lido	Xx	Xx	X.XX	X.XX, X.XX	
	Control	Xx	Xx	X.XX	X.XX, X.XX	
	Difference	-	-	X.XX	X.XX, X.XX	X.XX

Note: Subjects with a missing MMVS have their values imputed using BOCF up to Month 6.

Note: Responder is defined as a subject with an improvement of at least one grade on the MMVS from baseline.

Note: Responder rate is calculated as the number of Responders at the visit of interest divided by the number of subjects in the FAS population for the specific treatment group.

Note: P-values for the difference in proportions are based on the Fisher's Exact test.

Note: 95% Confidence Intervals are two-sided confidence intervals calculated using the exact interval.

Table A 17. MMVS responder rate by treatment and side of the face at Month 6, Blinded Evaluator (PP)

As Table A 16 (only Left and Right Side Combined)

Note: No imputation is used for PP analysis. Only subjects with complete data are included.

Note: Responder is defined as a subject with an improvement of at least one grade on the MMVS from baseline.

Note: Responder rate is calculated as the number of Responders at the visit of interest divided by the number of subjects in the PP population for the specific treatment group.

CCI

 GALDERMA	Title Statistical Analysis Plan 43CH1507	Doc id MA-32268
--	---	----------------------------------

Table A 18. Sensitivity analysis for the MMVS responder rate by treatment and side of the face at Month 6, Blinded Evaluator (FAS)

As Table A 16 (only Left and Right Side Combined)

Note: Missing MMVS values are handled using multiple imputation methods.

Note: Responder is defined as a subject with an improvement of at least one grade on the MMVS from baseline.

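### Randomisation is stratified by site, but the visible primary p-value comes from an unstratified Fisher test; a site-stratified CMH test is a small gain that needs no extra data

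*SAP*

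**What the plan says.** SAP 1.1.2 states: "The randomization will be stratified by site". Protocol 4.4.1 gives the 3:1 ratio and names no stratification factor. The number of sites is not fixed: "The study will be performed at approximately 5 sites in China and approximately 168 subjects will be enrolled" (Protocol 4.2).

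The notes to SAP Table A 16, which reports the primary comparison, say: "P-values for the difference in proportions are based on the Fisher's Exact test". They add: "95% Confidence Intervals are two-sided confidence intervals calculated using the exact interval". No stratification is mentioned. SAP 3.3.3 says of site: "Site effects will be explored by using descriptive statistics of the treatment effects by site". Figure A 1 plots the responder difference by site, and Table A 19 corrects for baseline MMVS rather than for site. For multiple imputation, SAP 3.3.2 says: "The imputed datasets will be analyzed using the methodology described for the primary analysis of responder rates at Month 6".

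The description of the test in SAP 3.3.3 and Protocol 10.4, the closing notes to Tables A 17 to A 19, and the sample-size text are blacked out in whole or in part. The statements here concern the visible text only.

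**The concern.** When randomisation is stratified, the usual analysis compares the arms within strata. Here the primary test pools all sites. If responder rates differ between sites, for example because injectors or evaluators differ, the pooled test counts that variation as noise that the design has already balanced out. Fisher's test is also discrete and runs below its nominal level even when sites are alike.

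Both effects make the test conservative. What is at stake is some power and agreement between design and analysis, not a false positive. Multiple imputation raises a second, practical point. Fisher's test gives a p-value without an estimate and variance to pool, and the visible text does not say how the five p-values would be combined.

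**Working it through.** **Inputs from the documents.** 148 randomised 3:1: 148 × 3/4 = 111 treated and 148 × 1/4 = 37 controls, as the protocol synopsis states. About 5 sites. US Month 2 responder rates of 133/150 = 88.7% and 8/50 = 16.0% (Protocol 2.4.2). Fisher's test on 133/150 v 8/50 gives p = 2 × 10⁻²¹, in line with the reported p < 0.001. The planned power cannot be reproduced because its basis is blacked out.

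**Assumptions.** Two-sided α = 0.05; between-site SD on the logit scale of 0, 0.5 or 1.0; treated rates below 88.7%; site layouts. Three layouts were used: 5 equal sites, 5 unequal sites, and 8 sites of which several have 0-2 controls. The stated rates are averages over sites.

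**Fisher, exact enumeration of the 111 × 37 outcomes, sites alike.** Size is 3.47% at a common rate of 10%, 3.77% at 16%, 3.94% at 30% and 3.55% at 50%. Power against 16% is 79.2% (treated rate 40%), 97.0% (50%), 99.9% (60%) and 100% (75% and above).

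**CMH by site.** Site i has n₁ᵢ treated, n₀ᵢ controls, Nᵢ in total, mᵢ responders and aᵢ treated responders:

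- Eᵢ = n₁ᵢmᵢ/Nᵢ
- Vᵢ = n₁ᵢn₀ᵢmᵢ(Nᵢ − mᵢ)/[Nᵢ²(Nᵢ − 1)]
- χ² = [Σ(aᵢ − Eᵢ)]²/ΣVᵢ on 1 df, without continuity correction

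Simulation used 200,000 trials per size scenario and 100,000 per power scenario. Ranges run over layouts and over random or fixed site effects:

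| Scenario | Site SD | Fisher | CMH |
|---|---|---|---|
| Size, 16% in both arms | 0 | 3.7-3.8% | 4.6-5.0% |
| | 0.5 | 3.4-3.6% | 4.6-5.0% |
| | 1.0 | 2.9-3.1% | 4.6-5.0% |
| Power, 40% v 16% | 0 | 79-80% | 80-81% |
| | 0.5 | 77-79% | 81-83% |
| | 1.0 | 77-79% | 84-87% |
| Power, 50% v 16% | 0 and 0.5 | 97% | 98% |
| | 1.0 | 97-98% | 98-99% |
| Power, 60% v 16% | all | ≥ 99.7% | ≥ 99.7% |
| Power, 88.7% v 16% | all | 100% | 100% |

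**Sensitivity to the site model.** The SD 1.0 row at 40% v 16% depends on how site effects are set. With 5 equal sites, one fixed arrangement gives 76.8% v 87.3%. Evenly spaced fixed effects give 82.9% v 86.3%. Reading 40% and 16% as typical-site rates gives 67.6% v 75.9%. The gain therefore runs from 86.3 − 82.9 = 3.4 to 87.3 − 76.8 = 10.5 points, always in favour of CMH.

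**Where the gain comes from.** At 40% v 16% with SD 0, an unstratified chi-square test has 80.7% power and CMH 80.6%, so the whole gain over Fisher (79.4% in the same run) comes from leaving the discrete test. With random site effects of SD 0.5, the figures are Fisher 78.7%, unstratified chi-square 80.5% and CMH 81.7%: 1.8 points from discreteness and 1.2 from stratifying.

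**Version of CMH.** The continuity-corrected version has 73.4% power at 40% v 16% (SD 0), below Fisher's 79.4%, so the version must be named.

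**Test and interval disagreeing.** The share of trials with p < 0.05 while an unstratified exact unconditional 95% interval includes 0, at 40% v 16%, is 6-7% with Fisher and 7-17% with CMH if the interval is built on the raw difference, and 12-14% and 13-24% if on the score statistic. With CMH it is at most 0.5% at 60% v 16% and 0% at 88.7% v 16%. Which construction the SAP intends is not visible.

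**Multiple imputation.** With 5 equal sites, 5 imputations without site in the model and 5-15% missing completely at random (assumed), pooling Σ(aᵢ − Eᵢ) and ΣVᵢ by Rubin's rules gave size 4.5-4.9%. Pooling a Wilson-Hilferty transform of the chi-square gave 5.1-5.4%.

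**The case against.** The strongest reply is that nothing is broken. Fisher's test is valid, a size below 5% is no fault in a superiority trial, and at every rate the documents report the two tests agree. The US study also found significant responder differences through Month 12, so a Month 6 treated rate near 40% is not the expected case. All of this stands, and it is why the point is minor.

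Two further points stand in part. When sites are alike, the gain owes nothing to stratifying. When they differ, its size depends on an assumed site model, although its direction does not. A site-adjusted analysis may also sit in the blacked-out text; as a supportive analysis, it would not change the test that Table A 16 names for the primary p-value.

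The remedy has a price as well. It replaces an exact test with an asymptotic one and sets a stratified p-value beside an unstratified interval, so the two disagree somewhat more often. In the layouts tried, CMH stayed at or just below 5%. The disagreement is confined to effects far smaller than the US study's. A matching stratified interval would not be a clear improvement: the Mantel-Haenszel risk difference with Sato's variance covered only about 93% at 88.7% v 16%. A more modest course would leave Fisher primary and add CMH as supportive. That is defensible, but the decisive test would then still ignore the stratification.

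**Conclusion.** The concern holds as a minor point of efficiency and consistency. The visible primary test ignores the one factor that the randomisation is stratified by. It runs at about 3-4% rather than 5% near a 16% common rate, and CMH by site would run at 4.6-5.0%.

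The power gain is nil at 88.7% v 16% and about 1 point at 40% v 16% when sites are alike. It reaches roughly 3 to 10 points only with a 40% treated rate and strong site differences. These figures rest on two-sided α = 0.05, on assumed between-site spreads and layouts, and on a Month 2 control rate from a US population used for Month 6 in China. The trial's expected conclusion does not depend on the choice. Confidence is medium, because the text describing the primary test is partly blacked out.

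**What to change.** - **Primary test.** In SAP 3.3.3 and the p-value note to Table A 16, name the asymptotic CMH test stratified by site, without continuity correction. Keep the unstratified Fisher p-value as a supportive line.
- **Small sites.** Fix in advance, without looking at outcomes, that sites with fewer than 4 controls or only one arm are pooled into one stratum, adding the next smallest site if that stratum still has fewer than 4 controls. The threshold is a convention. Size is 4.6-4.9% with the rule and 4.8-5.0% without it. Its purpose is to keep one-arm sites in the test.
- **Interval.** Keep the planned exact interval as the main interval. State that the CMH p-value decides superiority and that the interval describes the size of the effect. A site-stratified risk difference may be shown as supportive only.
- **Imputed datasets.** In SAP 3.3.2 and Table A 18, pool D = Σ(aᵢ − Eᵢ) and V = ΣVᵢ over the five datasets by Rubin's rules, with total variance equal to the mean of V plus (1 + 1/5) times the between-imputation variance of D.

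The cost is a few sentences, with no new data or subjects. The sponsor should also check whether the blacked-out sample-size text (SAP 4, Protocol 10.10) or Protocol 10.4 names the test, and align them.

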Electronically signed in the document management system within Q-Med quality management system

Clinical Project Manager, Q-Med AB
 PPD

Electronically signed in the document management system within Q-Med quality management system

Study Statistician, Q-Med AB
 PPD

Electronically signed in the document management system within Q-Med quality management system

	Title 43CH1507 Perlane Lido midface study protocol	Doc id MA-30843
--	--	---------------------------

2016-09-07 11:57

Effective date:

Signed Agreement of the Clinical Study Protocol

CTN:

43CH1507

Title of the CSP:

A randomized, multi-center, evaluator-blinded, no-treatment controlled study to evaluate the efficacy and safety of Restylane Perlane Lidocaine for correction of Midface Volume Deficit and/or Midface Contour Deficiency

I, the undersigned, have read and understand the protocol specified above, and agree on the contents. The study protocol, the Clinical Trial Agreement and the additional information given in the Instruction For Use for Restylane Perlane Lidocaine will serve as a basis for co-operation in this study.

Principal Investigator

Printed name

Signature

Date

Study site

Version: 4.0

2016-09-07 11:57

Effective date:

Effective

Version: 4.0

 GALDERMA	Title: 43CH1507 Perlane Lido midface study protocol	Doc id: MA-30843
--	--	-----------------------------------

Synopsis

Title of study:	A randomized, multi-center, evaluator-blinded, no-treatment controlled study to evaluate the efficacy and safety of Restylane Perlane Lidocaine for correction of Midface Volume Deficit and/or Midface Contour Deficiency
Clinical Trial Number:	43CH1507
Countries involved, number of sites/country, number of subjects:	
The study will be conducted at approximately 5 sites in China.
 
Group A: Up to 20 subjects (2 first treated subjects per Treating Investigator) will be enrolled as group A. These subjects will all receive treatment with Restylane Perlane Lidocaine (Perlane-Lido).
 
Group B: Evaluator treatment-blind group with approximately 148 subjects will be randomized in a 3:1 ratio to treatment group or no-treatment control group, i.e., 111 subjects assigned to the Treatment Group and 37 subjects assigned to the Control Group.

Co-ordinating Investigator:	PPD

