4.7 Schedule of events

Table 1. Schedule of Events for Group A and Treatment Group

	Group A and Treatment Group					
	Screening ^a	Baseline ^a / Initial treatment	Follow-up / Optional Touch-up	Follow-up ^b	Follow-up	Final visit / Early termination
	D-21 to D1	D1	4W(±3d) after randomization	4W(±3d) after touch-up	3M(±1w), 6M(±1w) and 9M (±2w) after last treatment	12M (±2w) after last treatment
Informed consent	X					
Height, Demography	X					
Weight	X	X	X	X	X	X
Medical history & concurrent diseases	X	X				
Concomitant medication/procedures	X	X	X	X	X	X
Vital signs		X ^c				
Laboratory tests	X		X		X ^c	X ^f
ECG	X					
Pregnancy test		X ^c	X ^c			X
Inclusion and Exclusion criteria	X	X				
Randomization		X				
Treatment		X	X			
MMVS (Blinded Evaluator)	X	X ^c			X	X
CCI						
Photography		X ^c	X ^{c, d}	X	X	X

Device deficiencies		X	X			
Assessment of AE	X	X	X	X	X	X
Study termination						X

a) Screening visit and baseline visit can be combined to one visit if feasible.

b) Only for subject receive touch-up treatment.

c) Prior to treatment, if treat performed.

CCI

e) Only performed at 6M.

f) Only performed at early termination if termination occurs before 6 months visit after last treatment

Table 2. Schedule of Events for Control Group

Activity	Control Group									
	Screening ^a	Baseline ^a	Follow-up	Follow-up	Follow-up /Treatment	Follow-up /Optional Touch-up	Follow-up ^b	Follow-up	Final visit / Early termination	
	D-21 to 1	D1	4W(±3d) after randomization	3M (±1w) after randomization	6M(±1w) after randomization	4W(±3d) after 6M treatment	4W(±3d) after touch-up	3M (±1w) after last treatment	6M (±1w) after last treatment	
Informed consent	X									
Height, Demography	X									
Weight	X	X	X	X	X	X	X	X	X	
Medical history & concurrent diseases	X	X								
Concomitant medication/procedures	X	X	X	X	X	X	X	X	X	

Vital signs		X			X ^c					
Laboratory tests	X				X ^c	X				X
ECG	X									
Pregnancy test		X			X ^c	X ^c				X
Inclusion and Exclusion criteria	X	X								
Randomization		X								
Treatment					X	X				
MMVS (Blinded Evaluator)	X	X		X	X ^c			X		X
CCI										
Photography		X	X ^d	X	X ^c	X ^c	X	X		X
CCI										
Device deficiencies					X	X				
Assessment of AE	X	X	X	X	X	X	X	X		X
Study termination										X

a) Screening visit and baseline visit can be combined to one visit if feasible.

b) Only for subject receive touch-up treatment.

c) Prior to treatment, if treat performed.

CCI

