10.5 Safety Analysis

CCI

A

similar summary will also be presented by severity. A graph will be generated to illustrate the incidence over time. Data from the Perlane-L group will be pooled with the no-treatment group.

All AEs will be coded according to MedDRA.

All AEs will be summarised by system organ class (SOC), preferred term (PT) and treatment. Since the no-treatment control group will receive treatment at the month 6 visit, only AEs occurring up until that time point will be included in this presentation, for both groups. Furthermore, all AEs will also be summarised by SOC and PT using the Perlane-L group for the whole study period, and also using the no-treatment group for the study period following their treatment at Month 6.

Related AEs will be summarised by SOC, PT and intensity. In addition, for related AEs the number of days to onset and the duration of event will be summarised by SOC and PT using mean, SD, min, max and median. Action taken for related AEs will also be summarised. Data from the Perlane-L group will be pooled with the no-treatment group.

Serious AEs will be listed.

Non related AEs will be summarised by SOC, PT, and intensity. This will be done as described for all AEs, i.e. based on the following subsets of data: first 6 months following treatment by treatment, the Perlane-L group for the whole study, and the no-treatment group for the period following their treatment.

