3.4.2 Adverse events

All AEs will be coded according to MedDRA. All AE summaries defined below will be presented by treatment (no treatment at baseline vs. all treated subjects (at baseline and Month 6)).

The number of subjects with AEs related to study product or injection procedure as well as the number of events will be summarized by SOC and preferred term (PT). In addition, AEs related to study product or injection procedure will be summarized by SOC, PT and intensity. The number of days to onset and the duration of related AEs will be summarized by SOC and PT using mean, SD, min, max and median.

Serious AEs and device deficiencies will be listed, if applicable.

Non related AEs will be summarized by SOC, PT, and intensity.

CCI

[figure not shown]

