TEAEs unrelated to product and/or injection procedure	xx	xx.x	xx	xx	xx.x	xx
of which were serious	xx	xx.x	xx	xx	xx.x	xx
Subjects with no AE reported	xx	xx.x	-	xx	xx.x	-

Note: Treatment with Perlane-Lido columns include data from subjects in the Perlane-Lido group after their initial treatment at baseline, as well as data from subjects in the Control group after their initial treatment at Month 6.

% = $100 * n/N$

 GALDERMA	Title Statistical Analysis Plan 43CH1507	Doc id MA-32268
---	--	----------------------------------

Table A 35. Related TEAEs by MedDRA System Organ Class, Preferred Term, and intensity (Safety)

Primary System Organ Class Preferred Term	Intensity	No treatment at baseline N=xx		Treatment with Perlane-Lido N=xx	
		Events	Subjects	Events	Subjects
Any related AE	Total	Xx	Xx (xx.x)	Xx	Xx (xx.x)
	Mild	Xx	Xx (xx.x)	Xx	Xx (xx.x)
	Moderate	Xx	Xx (xx.x)	Xx	Xx (xx.x)
	Severe	xx	Xx (xx.x)	xx	Xx (xx.x)
SOC1	Total	Xx	Xx (xx.x)	Xx	Xx (xx.x)
	Mild	Xx	Xx (xx.x)	Xx	Xx (xx.x)
	Moderate				
	Severe				
PT11	Total				
	Mild				
	Moderate				
	Severe				
PT12	Total				
	Mild				
	Moderate				
	Severe				
SOC2	Total				
	Mild				
	Moderate				
	Severe				
PT21	Total				

Note: Treatment with Perlane-Lido columns include data from subjects in the Perlane-Lido group after their initial treatment at baseline, as well as data from subjects in the Control group after their initial treatment at Month 6.

% = $100 * n/N$

 GALDERMA	Title Statistical Analysis Plan 43CH1507	Doc id MA-32268
---	---	----------------------------------

Table A 36. Duration (days) of related TEAEs by MedDRA System Organ Class and Preferred Term (Safety)

	No treatment at baseline N=xx							Treatment with Perlane-Lido N=xx						
	Ongoing	n	Mean	SD	Min	Median	Max	Ongoing	n	Mean	SD	Min	Median	Max
General disorders and administration site conditions														
Injection site xxx														
Injection site xxx														
ALL														

Note: Treatment with Perlane-Lido columns include data from subjects in the Perlane-Lido group after their initial treatment at baseline, as well as data from subjects in the Control group after their initial treatment at Month 6.

% = 100*n/N

Table A 37. Time to onset (days) of related TEAEs, by MedDRA System Organ Class and Preferred Term (Safety)

	No treatment at baseline N=xx							Treatment with Perlane-Lido N=xx						
	n	Mean	SD	Min	Median	Max	n	Mean	SD	Min	Median	Max		
General disorders and administration site conditions														

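### The pooled Perlane-Lido adverse-event column keeps treated controls in the denominator after their follow-up has ended, so percentages for related events starting more than 6 months after the last injection are understated

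*SAP*

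**What the plan says.** SAP 3.4.2 sets two columns for adverse events: "All AE summaries defined below will be presented by treatment (no treatment at baseline vs. all treated subjects (at baseline and Month 6". The notes to Tables A 34 to A 37 define the treated column as Treatment Group data after the baseline injection, "as well as data from subjects in the Control group after their initial treatment at Month 6". Tables A 34 and A 35 give the percentage of subjects as 100*n/N.

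Protocol 4.7 sets the last visit at "12M (±2w) after last treatment" in Table 1 (Group A and Treatment Group) and at "6M (±1w) after last treatment" in Table 2 (Control Group). Protocol 8.4.4 stops adverse-event reporting at the last scheduled visit. Protocol 8.4.6 extends follow-up only for related events already ongoing at study end, so it adds no new onsets.

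For related events, Protocol 10.5 already planned one combined presentation: "Data from the Perlane-L group will be pooled with the no-treatment group". For all adverse events it had separate summaries of the treated arm over the whole study and of controls after their Month 6 treatment. SAP section 5 replaces those with the two-column layout.

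**The concern.** The two cohorts in the treated column are observed for different lengths of time after injection, and a crude percentage takes no account of that. In months 6 to 12 after the last injection, treated controls cannot contribute an event but still count in the denominator. In the visible text, no adverse-event table splits by time since injection or by randomised arm, and none uses person-time.

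The safety objective (Protocol 3.3, SAP 1.2.3) covers the whole study. The protocol's account of the earlier US midface trial includes a related serious event of delayed type: "One subject reported implant site inflammation (late onset inflammatory reactions) in both cheeks at separate times". If such events occur here after month 6, the percentage a reader takes from the table will be too low.

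**Working it through.** **Inputs**
- Group sizes: "111 subjects assigned to the Treatment Group and 37 subjects assigned to the Control Group" (Protocol synopsis). SAP 1.1.2 gives about 148 randomised 3:1. Check: 148 × 3/4 = 111 and 148 × 1/4 = 37, so the stated split reproduces.
- Scheduled follow-up after last treatment: 12 months (Treatment Group) and 6 months (treated controls).
- u = number of controls who take the Month 6 treatment. The documents offer it without giving an expected uptake, so u is an assumption between 0 and 37.
- N is printed only as a placeholder. That it counts every injected subject follows from the column definition.

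**Step 1. A row whose events all start more than 6 months after last injection.** If x subjects are affected, the table prints x/(111+u), while the percentage among those who could be observed is x/111. The relative understatement is 1 − 111/(111+u) = u/(111+u).

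| Uptake (assumed) | u | u/(111+u) |
|---|---|---|
| 100% | 37 | 37/148 = 25% |
| 75% | 27.75 | 27.75/138.75 = 20% |
| 50% | 18.5 | 18.5/129.5 = 14% |
| 0% | 0 | 0% |

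Example at full uptake: 3 affected subjects print as 3/148 = 2.03% instead of 3/111 = 2.70%.

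**Step 2. A row covering events at any time, which is what the tables print.** Let p be the 12-month risk and s the share of affected subjects whose only event is late. Assume the same risk by time since injection in both cohorts and no withdrawals. The expected printed value is

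[111p + u·p(1 − s)]/(111 + u) = p[1 − s·u/(111+u)],

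so the understatement is s × u/(111+u). At full uptake:
- s = 0.5 (risk even over 12 months): 0.5 × 25% = 12.5%
- s = 0.1: 0.1 × 25% = 2.5%
- s = 0 (all onsets within 6 months): 0%

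**Step 3. Sensitivity.** Both schedules run from the last treatment, so a touch-up shifts both cohorts by about 4 weeks and leaves the 6-month gap unchanged. The 25% is for planned numbers. If only 105 of the Treatment Group were injected and all 37 controls were, it would be 37/142 = 26.1%.

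**Step 4. Table A 37 (time to onset).** SAP 1.5 derives onset as start date minus Day 1, and Day 1 in the control schedule is baseline. Read literally, a control's same-day reaction to the Month 6 injection is given an onset of about 6 months. Late onsets therefore cannot be picked out of this table.

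**The case against.** The strongest reply is that no planned table prints a late-event rate. Tables A 34 and A 35 count subjects with an event at any time, and the documents expect most related events early. Protocol 8.4.8 has injection reactions starting on the day of treatment and resolving in 2 to 7 days, and the appended instructions for use describe inflammation starting shortly after injection or up to several weeks later. The US-trial case is called late onset but no time is given, so it does not show onset after month 6. Tables A 3 and A 4 show how many subjects remain at each visit, safety data are listed by subject (SAP 3.1), and serious events are listed, so a serious late reaction would not be hidden.

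All of this stands, and it limits the size of the problem. It does not remove it. The accountability tables give a denominator without late-event counts, and the listings permit a re-analysis that the visible plan does not include.

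Four stronger readings are tempting but not supported:
- A reader might infer that the overall related-event percentage is 25% too low. Step 2 shows that this needs every affected subject to be late.
- A reader might infer that SAP section 5 introduced the pooling of related events. Protocol 10.5 already pooled them; section 5 removed only the separate all-event cohorts.
- A reader might infer that the visits after month 6 exist to detect late reactions, or that confidence limits will be too favourable. Blinded MMVS ratings are also scheduled at 9 and 12 months, safety is summarised descriptively (SAP 3.4), and the visible adverse-event tables plan no intervals.
- A reader might infer that Table A 37 cuts treated controls off at 6 to 7 months after their own injection. Under the Day 1 rule, it instead adds spuriously late values for them.

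**Conclusion.** The concern holds for related events starting more than 6 months after the last injection, in the pooled column of Tables A 34 and A 35. At planned numbers the understatement is 25% for an entirely late row if every control is treated, falling to 20% and 14% at 75% and 50% uptake. For percentages at any time it is that figure times the late share, so total related-event percentages will probably move little, and early injection reactions not at all. The sizes assume that N counts all injected subjects, that risk by time since injection is equal in the two cohorts, and that there are no withdrawals. This is a known downward bias in descriptive safety tables. It does not touch the efficacy conclusion, and it is cheap enough to remove that it should be.

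**What to change.** In SAP 3.4.2 and Tables A 34 and A 35, do one of the following.

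(a) Preferred: pool related treatment-emergent events only up to 6 months after last injection, with N = all injected subjects. Report months 6 to 12 for the Treatment Group alone, with N = subjects still followed at 6 months after last treatment.

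(b) Simpler: add separate columns for the Treatment Group (whole study) and treated controls (after their injection), a layout that Table A 32 already uses. This is not equivalent to (a), because it neither isolates months 6 to 12 nor uses the number still followed then.

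For Table A 37, amend SAP 1.5 so that onset is counted from the subject's own injection and not from Day 1, then apply the same split.

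The cost is SAP wording, one revised derivation and longer tables, with a smaller N for the late period. No extra data, visits or subjects are needed.
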